6.2.1. Rationale for Exclusion of Certain Study Candidates

Conflict of interest in study participants is outlined in Criteria [9] and [10]. Excluded medical conditions, medication intolerance, and concomitant medication use that may constitute a risk for the subject and/or may confound the assessment of study endpoints are described in Criteria [11] through [32].

6.3. Lifestyle and/or Dietary Requirements

Throughout the study, subjects may undergo medical assessments and review of compliance with requirements before continuing in the study.

6.3.1. Meals and Dietary Restrictions

Subjects will be required to fast overnight for at least 8 hours before taking a SC or IV dose of LY3298176, and when clinical safety laboratory samples are taken (see Schedule of Activities [Section 2]). Water may be consumed freely. Standard meals will be administered in the CRU.

6.3.2. Caffeine, Alcohol, and Tobacco

No alcohol will be allowed for at least 24 hours before each CRU admission and each outpatient visit, and throughout the duration of each CRU visit. Between CRU visits, daily alcohol consumption should not exceed 3 units for males and 2 units for females (a unit is defined in Exclusion Criterion [25], Section 6.2). No nicotine use will be permitted while in the CRU. While not resident in the CRU, subjects must consume no more than 10 cigarettes or the equivalent per day.

Subjects will be allowed to maintain their regular caffeine consumption throughout the study period.

6.3.3. Activity

Subjects should not engage in strenuous physical exercise or activities from 48 hours prior to the first dose, and for duration of the study. When certain study procedures are in progress at the site, subjects may be required to remain recumbent or sitting.

6.4. Screen Failures

Subjects who do not meet the criteria for participation in this study (screen failure) may not be rescreened.

7. Treatment

7.1. Treatment Administered

This study involves a comparison of drug product LY3298176, for injection that is being used in the Phase 1 and ongoing Phase 2 trials to the intended solution formulation of LY3298176 drug product for Phase 3 trials over a planned dose range, administered by SC injection. In addition, the PK of a single IV dose of LY3298176 will be evaluated. [Table GPGE.7.1](#) illustrates the treatment regimens.

7.1.1. LY3298176 for Injection

LY3298176 for injection, 5 mg, is supplied as lyophilized formulation in a glass vial for SC and IV infusion administration. [CCI](#)

[REDACTED] The reconstituted product solution in the vial(s) may be held at room temperature and/or refrigerated (2°C to 8°C), and should be administered within 4 hours from the time of reconstitution. LY3298176 for injection, 5-mg vials, are intended for single-dose administration.

7.1.2. LY3298176 Solution Formulation Injection

LY3298176 injection is prepared by sterile compounding, and is for SC and IV administration.

[CCI](#)

[REDACTED] The LY3298176 drug product solution vials may be held refrigerated (2°C to 8°C) for not more than 72 hours. The drug product solution must be administered within 4 hours after it is removed from refrigerated (2°C to 8°C) storage. LY3298176 compounded sterile drug product vials are intended for single-dose administration.

All investigational product provided to the investigator will be stored in a secure location, and allocated and dispensed by appropriately trained persons. The allocation and dispensing of the investigational products will be fully documented and verified by a second person. Detailed records of the amounts of investigational product received, dispensed, and remaining at the end of the study will be maintained. Detailed instructions for the preparation and handling of LY3298176 will be provided by the Sponsor in a pharmacy manual.

Table GPGE.7.1 **Treatments Administered**

Treatment Name	LY3298176	LY3298176 Solution	Placebo to Match LY3298176 Solution
Dosage Formulation	Reference lyophilized powder in glass vial	Test solution formulation in a glass vial	Test solution formulation in a glass vial
Unit Dose Strength(s) / Dosage Level(s)	Each vial can deliver 5 mg LY3298176	Concentration ranging from 10 mg/mL to 30 mg/mL	Placebo
Route of Administration	Subcutaneous injection and intravenous infusion	Subcutaneous injection and intravenous infusion	Subcutaneous injection
Dosing Instructions	Single-dose administration	Single-dose administration	Single-dose administration

7.2. Method of Treatment Assignment

Part A: the treatment to be injected for each period will be determined according to a randomization schedule.

Part B: a fixed, single-arm treatment.

Part C: the treatment to be injected on a given treatment day will be determined according to a randomization schedule.

7.2.1. Selection and Timing of Doses

Part A: Subjects will be randomized to 1 of 2 treatment sequences to be administered over 2 consecutive study periods. Each treatment period will consist of the reference lyophilized formulation and a test-solution formulation. The sequence of treatments will be administered according to the randomization schedule. The doses will be administered at approximately the same time of the day during both periods. The actual time of all dose administrations will be recorded in the subject's electronic case report form (eCRF). Injections will be administered into the SC tissue of the abdominal wall.

Part B: A single, 0.5-mg IV dose of LY3298176 will be administered in the morning following an 8-hour, overnight fast. The actual start and stop time of IV dose administration will be recorded in the subject's eCRF.

Part C: Dosing will commence at approximately the same time of day at each dosing instance. The actual time of all dose administrations will be recorded in the subject's eCRF. All injections will be administered into the SC tissue of the abdominal wall. Injection sites will be alternated weekly between 4 sites (ie, right and left upper quadrants and right and left lower quadrants) on the abdominal wall.

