2.1. Study Schedule Protocol I8F-MC-GPGE, Part A

Procedure (Part A)	Screening	Periods 1 and 2												ET	Comments		
		Days	-28 to -2	-1	1	2	3	4	5	6	7	8	15	21	35 - 37 post dose period 1	35 - 37 post dose period 2	
Informed Consent	X																
Subject Admission to CRU			X														
Subject Discharge from CRU												X					Subjects may stay longer according to investigator discretion
Outpatient Visit	X												X	X	X	X	X
Investigational Product Administration					X												There is a minimum of 35 days washout period between doses for Period 1 and Period 2. Study drug will be administered SC after an overnight fast of at least 8 hours.
Medical History	X																
Height	X																
Weight	X	X												X	X	X	
Vital Signs (BP/PR/T) (supine)	X	X	P	24	48							X	X	X	X	X	Time points may be added for each study period, if warranted and agreed upon between Lilly and the investigator.

Procedure (Part A)	Screening	Periods 1 and 2														ET	Comments
Days	-28 to -2	-1	1	2	3	4	5	6	7	8	15	21	35 - 37 post dose period 1	35 - 37 post dose period 2		≥ 35 day washout between doses 1 and 2.	
Clinical Laboratory Tests	X	X								X			X	X	X	See Appendix 2 , Clinical Laboratory Tests, for details.	
Adverse Event		X	X	X	X	X	X	X	X	X	X	X	X	X	X		
Injection Site Reaction Assessment			P, 0, 6h, 12h	24h	48h											0-hour assessment should be performed within 5 minutes after subcutaneous injection. Additional assessments may be performed if deemed necessary by the investigator. Visual analog scale (VAS) score will be recorded	
PK Samples			P, 8h, 12h,	24h	48h	72h	96h	120h	144h	168h	336h	480h	X	X	X	Sampling times are relative to the start of dose administration (0 hr). Predose sample must be collected before dose administration. If a subject withdraws from the study prior to completion of scheduled PK sampling for a given period, every effort will be taken to draw an unscheduled blood sample for PK	

Procedure (Part A)	Screening	Periods 1 and 2														ET	Comments
Days	-28 to -2	-1	1	2	3	4	5	6	7	8	15	21	35 - 37 post dose period 1	35 - 37 post dose period 2		≥35 day washout between doses 1 and 2.	
																	assessment. This will not be required if a sample has already been taken within the previous 24 hours. For ET, a PK sample can be taken at any time during the visit timed close to the immunogenicity sample.

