2.3. Study Schedule Protocol I8F-MC-GPGE Part C

Procedure (Part C)	Screen	Prestudy	Treatment																		ET/Follow-up
Days	-28 to -2	Before -2	-1	1	2	3	4	8 ^a	9	10	15 ^a	16	17	18	22 ^a	23	24	25	57	≥92	
Informed consent	X																				
Admission to CRU ^c			X					X			X				X						
Discharge from CRU						X				X			X				X				
Outpatient visits to CRU		X												X				X	X	X	
Distribution of glucose meters, test strips, diary, and GM training		X																			
Distribution of additional test strips, and diary.								X			X				X						
Administer study drug ^d				X				X			X				X						
Medical history	X																				

Procedure (Part C)	Screen	Prestudy	Treatment																		ET/Follow-up			
			Days	-28 to -2	Before -2		-1	1	2	3	4	8 ^a	9	10	15 ^a	16	17	18	22 ^a	23	24	25	57	
Height and weight ^e	X					X	P					P			P				P					X
Physical examination	X																							
Medical assessment ^f	X						P					P			P				P					X
Vital signs (BP/PR/T) ^g (hours)	X				X	P	X	X				P	X	X	P	X	X		P	X	X			X
ECG ^h	X					P												P						X
PK sampling (hours)						P , 8h 2 4 h	48 h	72h	P			P , 8h 24 h	48 h	72 h	P , 8h 24 h	48 h	72 h	P , 8h 24 h	48 h	72 h	X		X	
Clinical laboratory tests ⁱ	X					P												P						X
AEs/concomitant medications	X					X	X	X				X	X	X	X	X	X	X	X	X	X	X	X	X
Injection site reactions ^b						P , 0, 6h, 12h 2 4 h					P , 0, 6h , 12 h	24		P , 0, 6, 12	24		P , 0, 6, 12	24						

Procedure (Part C)	Screen	Prestudy	Treatment																	ET/Follow-up			
			Days	-28 to -2	Before -2		-1	1	2	3	4	8 ^a	9	10	15 ^a	16	17	18	22 ^a	23	24	25	57
Pharmacogenomic sample								X															
Immunogenicity								P							P							X	X

Abbreviations: AEs = adverse events; BP = blood pressure; CRU = clinical research unit; ECG = electrocardiogram; ET = early termination; GM = glucose monitoring; h = hours; P = Predose; PK = pharmacokinetic(s); PR = pulse rate; T= temperature.

^a Dosing day – subjects will be admitted to CRU the day prior to dosing.

^b Visual analog scale (VAS) score will be recorded

^c For each CRU admission, subjects must remain at the CRU at least 72 hours postdose or per medical judgment.

^d Study drug will be administered after an overnight fast of at least 8 hours.

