^e Height measured at screening only. Weight will be measured twice in a consistent way, each predose. Scale needs to be calibrated (refer to Section 9.4.4).

^f Medical assessment will include a physical examination.

^g Vital signs(BP/PR/T) measurements: for each dose day: predose, 24 hr, 48 hr, and on or after Day 92 (follow-up/ET).

^h Single local safety ECGs will be measured at screening, predose Day 1, predose Day 22, predose Day 50 and follow-up/ET to take place on or after Day 92 (follow-up). Electrocardiograms must be recorded before collecting any blood for safety or PK samples and close to the time of the blood draw. Subjects must be supine for approximately 5 to 10 minutes before ECG collection and remain supine, but awake, during ECG collection.

ⁱ Clinical safety laboratory measures include chemistry, hematology, and urinalysis panels. Blood samples will be taken predose on all dosing days. Subjects will be required to fast for at least 8 hours before each blood sample is drawn.

3. Introduction

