3.3. Benefit/Risk Assessment

The nonclinical data and preliminary clinical data (See Section 3.2) from Study GPGA support further clinical development for LY3298176.

Predicted exposure multiples were derived from repeat-dose toxicology studies, using the highest proposed clinical dose of 15 mg/week. CCI [REDACTED]

[REDACTED] The effects in rats and monkeys included decreases in body weight and/or body weight loss, decreases in food consumption, and dehydration. All of the changes were consistent with, or secondary to, GLP-1 pharmacology, and were easily monitored in clinical studies. Furthermore, there was no evidence of target organ toxicity in either species. For more information, reference the Investigator's Brochure (IB).

No clinically significant safety or tolerability concerns were identified up to the highest single dose level of 8 mg or following 4 QW doses titrated up to 10 mg in Study GPGA. Based on this information, doses to be administered in Study GPGE will be tolerable to healthy subjects.

Any identified potential risks are similar with the risks associated with currently available long-acting GLP-1 receptor agonists (See Section 3.2), are considered to be manageable, and are able to be monitored.

More information about the known and expected benefits, risks, serious adverse events (SAEs) and reasonably anticipated AEs of LY3298176 is found in the compound IB.

4. Objectives and Endpoints

Table GPGE.4.1 shows the objectives and endpoints of the study.

Table GPGE.4.1 Objectives and Endpoints

Objectives	Endpoints
Part A: 
 Primary: To evaluate the PK of a single SC dose of LY3298176, administered as solution formulation (test) versus lyophilized formulation (reference) in healthy subjects. Secondary: To investigate the safety and tolerability of LY3298176, administered to healthy subjects. 	
 PK parameters, including AUC and C_{max}, AEs and injection site reactions
Part B: 
 Primary: To evaluate the PK of a single IV dose of LY3298176 in healthy subjects. Secondary: To investigate the safety and tolerability of LY3298176, administered to healthy subjects via IV formulation. 	
 PK parameters, including AUC AEs

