Part C: 
 Primary: To evaluate the safety and tolerability of LY3298176, following multiple SC weekly doses of a solution formulation administered in healthy subjects. Secondary: To evaluate the PK of LY3298176, administered as a solution formulation. 	
 AEs and injection site reactions PK parameters including AUC and C_{max}

Abbreviations: AEs = adverse events; AUC = area under the drug plasma concentration versus time curve;

C_{max} = maximum observed concentration; IV = intravenous(ly); PK = pharmacokinetic(s); SC = subcutaneous(ly).

5. Study Design

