10.3.1.3. Injection Site Reaction

For Part A and Part C, incidence of erythema, induration, pain, itching, and swelling will be listed and summarized by treatment.

The post-injection pain score will be summarized by treatment. Additional analyses may be performed, if appropriate.

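### Part C's scheduled injection-site and VAS checks end 24 h after each dose, against 48 h in Part A, although the endpoint is primary in Part C and secondary in Part A

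*Protocol*

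**What the plan says.** Protocol Section 4 (Table GPGE.4.1) gives Part C this objective: "Primary: To evaluate the safety and tolerability of LY3298176, following multiple SC weekly doses of a solution formulation administered in healthy subjects". Its endpoint is "AEs and injection site reactions". For Part A the matching objective is one level lower: "Secondary: To investigate the safety and tolerability of LY3298176, administered to healthy subjects".

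The schedules differ in how long the site is followed:

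- **Part A (Section 2.1).** The row "Injection Site Reaction Assessment" is marked predose and at 0, 6, 12, 24 and 48 h, with VAS. A comment allows extra assessments if the investigator thinks them necessary.
- **Part C (Section 2.3).** The row "Injection site reactions" is marked predose and at 0, 6, 12 and 24 h for each dose, with VAS. It has no later time and no comment about extra assessments.

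Part C vital signs are taken "for each dose day: predose, 24 hr, 48 hr" (Section 2.3, footnote g), so study staff see the subject at 48 h after every dose.

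On the injection site itself, Section 7.2.1 states for Part C: "Injection sites will be alternated weekly between 4 sites (ie, right and left upper quadrants and right and left lower quadrants".

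For analysis, Protocol 10.3.1.3 says: "For Part A and Part C, incidence of erythema, induration, pain, itching, and swelling will be listed and summarized by treatment". It sets no time window. SAP 9.4.6 puts the injection-site assessment data into frequency tables, and SAP 9.4.7 summarises VAS by treatment. Neither says whether a reaction known only from an adverse event report is counted there.

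**The concern.** The shorter schedule sits on the part where the endpoint is primary, which is also the only part with repeated dosing. If a reaction first appears after 24 h, Part A would meet it with a scheduled look and a pain score up to 48 h; Part C would not. It would then have to be picked up through general adverse event recording. On the SAP wording it might appear in the adverse event tables but not in the injection-site tables.

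At stake is how completely Part C describes local tolerability, and whether a reader can set its injection-site table beside Part A's without noticing that the two were collected over different windows.

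**Working it through.** There is no planned figure to reproduce: the Part C sample size is stated not to rest on a statistical calculation (Protocol 10.1, SAP 7.2). The check is a comparison of the schedules.

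**1. Schedules side by side (Protocol 2.1, 2.3 and Section 4)**

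| | Part A | Part C |
|---|---|---|
| Objective served | Secondary | Primary |
| Doses per subject | 2 | 4 (Days 1, 8, 15, 22) |
| Checks per dose | 6 | 5 |
| Checks per subject | 2 × 6 = 12 | 4 × 5 = 20 |
| Last scheduled post-dose time | 48 h | 24 h |

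The reproduction of the Part C table in Appendix 9 shows the same times. Part C has more checks in total because it has more doses; the window after each dose is half as long.

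**2. Share of the weekly interval covered in Part C**

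24/168 = 14.3% now; 48/168 = 28.6% with a 48-h check.

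This share should not be compared with Part A, where 48 h out of at least 35 days (840 h) is 5.7%. The relevant contrast is 24 h against 48 h after a dose.

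**3. Injections concerned (3:1 allocation, Protocol 10.1)**

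- 12 completers: 9 active × 4 doses = 36 active injections.
- 16 enrolled: 12 active × 4 doses = 48 active injections.

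**4. What the predose check can recover**

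Predose site checks are listed on Days 8, 15 and 22. If they include the previous week's site, the first three doses get a look at about 168 h: 27 of 36, or 36 of 48 active injections. If they cover only the site about to be injected, none do. The protocol does not say which. On either reading the fourth dose, on Day 22, has no scheduled site check after Day 23: 9 of 36, or 12 of 48.

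**5. Could any late-onset reaction plausibly occur? (assumption only)**

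The documents give no late-onset rate. Let p be the chance per injection that a reaction first appears at 24-48 h. The chance of at least one in the active arm is 1 - (1 - p)^n. Independent injections give n = 36 or 48. If a subject's four injections behaved identically, n would be the number of subjects, 9 or 12.

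| Assumed p | n = 9 | n = 12 | n = 36 | n = 48 |
|---|---|---|---|---|
| 1% | 9% | 11% | 30% | 38% |
| 2% | 17% | 22% | 52% | 62% |
| 5% | 37% | 46% | 84% | 92% |
| 10% | 61% | 72% | 98% | 99% |

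These are chances that a reaction would lack a scheduled check, not that it would go unrecorded.

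**6. Feasibility of a 48-h check**

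Dose days 1, 8, 15 and 22 plus two days are Days 3, 10, 17 and 24. All four are existing Part C study days with vital signs. Footnote c of Section 2.3 requires a stay of at least 72 h, while the discharge row and Section 5.1 point to discharge at 48 h (Day 3 after the first dose). Those passages need reconciling, but the subject is at the unit at 48 h under both.

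**The case against.** The strongest reply is that little is lost.

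- Adverse events are part of the same primary endpoint, and the Part C adverse event row continues past 24 h, including the 48-h days.
- Injection-site reactions are adverse events of special interest (Section 9.4.5). A reaction once present is fully characterised and followed to resolution (9.4.6.1), and VAS may be taken when clinically indicated (9.4.6.1.1).
- A predose medical assessment that includes a physical examination is scheduled on every dosing day (Section 2.3, footnote f).

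This stands, and it limits the point. These provisions keep late reactions reportable. But the follow-up and the extra VAS start only once someone has noticed or reported something, and the general examination is not specified to include the earlier injection site. They are not equivalent to a scheduled, solicited score.

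Four stronger readings are tempting, and the documents do not support them:

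- **That late reactions are missed.** They can be recorded as adverse events; what they lack is a scheduled assessment.
- **That site rotation causes the gap.** The schedule row causes it. Rotation only makes the predose check an uncertain backstop, and no passage confines that check to the new site.
- **That a planned comparison is biased.** Both Part C arms are on the same schedule, with investigator and subject blinded. SAP Section 6 reports Part A and Part C in separate treatment columns, with 5-10 mg pooled for Part C, and SAP 9.4.13 plans no inferential safety analysis.
- **That the flag for clinically significant treatment-emergent antibodies is weakened.** SAP 9.4.8 asks for an associated moderate-to-severe reaction without limiting it to scheduled checks.

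**Conclusion.** The point holds as a gap in solicited ascertainment. Scheduled site and VAS checks end at 24 h in the part where the endpoint is primary and at 48 h where it is secondary, with no reason given. Part C injection-site incidence is therefore ascertained over a window half as long as Part A's. The gap applies to 36 to 48 active injections, and equally to placebo injections.

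How many reactions this affects cannot be derived from the documents; the table of chances above rests entirely on assumed rates. The conclusion also rests on reading SAP 9.4.6 as covering the scheduled assessments, since it does not say that reactions reported only as adverse events are added. If the sponsor already intends to add them, the tabulation concern falls away, but the difference in solicited checks remains.

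This is a worthwhile, inexpensive improvement to a small descriptive part of the study, not a flaw that undermines its conclusions.

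**What to change.** - **Protocol Section 2.3:** add a 48-h injection-site and VAS assessment on Days 3, 10, 17 and 24. Checks rise from 5 to 6 per dose, and from 20 to 24 per subject.
- **Same row:** state that the predose check on Days 8, 15 and 22 includes the previous week's site as well as the new one.
- **SAP 9.4.6 and 9.4.7:** summarise Parts A and C over the same 0-48 h post-dose window. List anything first found at the previous site a week later separately, under the dose given there. Say whether reactions reported only as adverse events enter the tables.
- **Protocol Sections 2.3 and 5.1:** reconcile the two statements on length of stay after each Part C dose.

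The cost is a few minutes of site time per dose when subjects are already at the unit. No new visit, blood sample or staff is needed. The reported Part C incidence may be slightly higher as a result. If the sponsor prefers to keep 24 h, the protocol should give the reason and the tables should state the different windows.

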7.3. Blinding

Parts A and B are open label. Part C is investigator- and subject-blinded.

In case of an emergency, the investigator has the sole responsibility for determining if unblinding of a subject's treatment assignment is warranted for medical management of the event. The subject's safety must always be the first consideration in making such a determination. If the

investigator decides that unblinding is warranted, it is the responsibility of the investigator to promptly document the decision and rationale and notify Lilly as soon as possible.

